5.1.1.2.2. Treatment Period

Randomization (Visit 2)

At Visit 2, eligible participants will perform all required baseline study procedures (including the collection of all baseline laboratory measures and questionnaires) prior to randomization and prior to taking the first dose of study drug. Participants should arrive to the clinic in the fasting state (after a period of approximately 8 hours without eating, drinking [except water], or any significant physical activity and before taking study drug(s)). The mental health questionnaires (Patient Heath Questionnaire-9 [PHQ-9], Columbia-Suicide Severity Rating Scale [C-SSRS], and Self-Harm Form) should be completed after the assessment for AEs.

Participants will receive an initial consultation with a qualified dietitian, according to local standards, to set lifestyle goals for caloric intake and physical activity (Sections 6.3.1 and 6.3.2).

Following randomization, study site personnel will demonstrate use of the autoinjector and observe the study participant inject the first dose of tirzepatide or placebo. The date and time of the first dose of study drug will be recorded on the electronic case report form (eCRF). Beginning at randomization, all participants will receive study drug according to the randomized treatment arm for the duration of the 52-week dose escalation and treatment period.

Treatment Period (End of Visit 2 to Visit 15):

During the treatment period, visits will occur every 4 weeks through 52 weeks. The participant should be fasting for all office visits. Weeks 28, 32, 40 and 48 are telephone visits.

Office visit procedures should be conducted according to the Schedule of Activities (Section 2), and will include

- weight, waist circumference, and vital signs measurements
- review of participant diary information (to include reinforcement and compliance assessments for study drug administration and lifestyle goals)
- administration of questionnaires
- laboratory testing
- drug dispensing, and

• collect AEs and concomitant medications.

Patient-Reported Outcomes (PROs) questionnaires should be administered as early as possible, prior to any other study procedures. All PROs should be completed before any other study procedures if the participant is not adversely affected by the fasting condition or completed after the participant has sufficiently recovered from the preceding visit procedures. Mental Health Questionnaires should be completed after the assessment of AEs.

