A placebo comparator was selected for this trial in accordance with regulatory guidance (FDA 2007; EMA 2016). In addition, all participants, regardless of treatment assignment, will receive lifestyle modification counselling consistent with current guidelines for weight management (Jensen et al. 2013). Specifically, participants will consult with a dietitian, or equivalent qualified delegate, throughout the study to achieve at least a 500 kcal/day energy deficit through a combination of caloric restriction and increased physical activity (see Section 6.3).

The planned duration of treatment for the primary endpoint at 52 weeks allows for a 40-week treatment period at the dose achieved 10 mg and 32-week treatment period at the dose achieved 15 mg following dose escalation. This duration is considered appropriate to assess the full effects and benefit/risk of each maintenance dose of tirzepatide compared with placebo on body weight.

The effects of drug cessation will be assessed in the 4-week safety follow-up/observational period.

To minimize the potential confounding effect of changes to concomitant medications, participants will be permitted to use concomitant medications that do not interfere with the assessment of efficacy or safety characteristics of the study treatments.

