7.4.2. Management of Participants with Gastrointestinal Symptoms

Participants who experience intolerable GI symptoms (for example: nausea, vomiting, or diarrhea) at any time during the study, should first be counselled on dietary behaviors that may help mitigate nausea and vomiting, (for example, eating smaller meals, splitting 3 daily meals into 4 or more smaller ones, and stopping eating when they feel full). If symptoms persist, the participant should be prescribed, at the investigator's discretion, symptomatic medication (for example, antiemetic or antidiarrheal medication). A temporary interruption of study drug for 1

dose is permitted, provided the participant has taken the last 3 weekly doses. Study treatment should be resumed at the assigned dose immediately, either alone or in combination with symptomatic medication (Appendix 9). Management of study drug after interruptions >1 dose is discussed in Section 8.1.2.

If intolerable GI symptoms (for example, nausea, vomiting, or diarrhea) persist despite the above measures, the investigator should contact Lilly to consider reinitiating study drug at the next lowest maintenance dose in a blinded fashion (for example, 15 mg and 12.5 mg reduced to 10 mg, 10 mg or lower reduced to placebo, the lower dose will be maintained for the rest of the study, with no re-escalation allowed).

If intolerable GI symptoms persist despite symptomatic treatment, temporary drug interruption, and resumption at a lower dose of study drug, the participant should be discontinued from the study drug. Only 1 dose reduction per participant will be permitted during the course of the study. All participants who discontinue study drug should continue to attend scheduled study visits. All dose adjustments will be managed through IWRS.

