10.2. Populations for Analyses

For purposes of analysis, the following populations are defined:

Table GPIA.4. Definition of population

Population	Description
Entered	All participants who sign informed consent.

Randomized	All participants who are randomly assigned a study treatment.	
Modified Intent-to-Treat	All randomly assigned participants who are exposed to at least 1 dose of study	
(mITT)	drug. Participants will be included in the treatment group they were	
	randomized to.	
Efficacy Analysis Set (EAS)	Data obtained during treatment period from mITT, excluding data after	
	discontinuation of study drug (last dose date + 7 days).	
Full analysis set (FAS)	Data obtained during treatment period from mITT, regardless of adherence to	
	study drug.	
Safety Analysis Set (SS)	Data obtained during the entire study from mITT, regardless of adherence to	
	study drug.	
Per Protocol Set (PPS)	Participants included in the randomized population who have completed Week	
	52 of study treatment without permanent discontinuation of IP and without	
	significant protocol deviations through Week 52 that would significantly	
	impact the primary objective.	
	Treatment group will be defined on the basis of the treatment the participants	
	actually receive.	

Abbreviations: EAS = Efficacy Analysis Set, FAS = Full Analysis Set, IP = investigational product; mITT = Modified Intent-to-Treat, PPS = Per Protocol Set, SS = Safety Analysis Set.

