enter Patients entered into a study are those who sign the informed consent form directly or

through their legally acceptable representatives.

ERB ethical review board

ERCP endoscopic retrograde cholangiopancreatography

FAS full analysis set

FSG fasting serum glucose

FSH follicle-stimulating hormone

GCP good clinical practice

GGT gamma-glutamyl transferase

GHO Global Health Observatory

GI Gastrointestinal

GIP glucose-dependent insulinotropic polypeptide

GIPR glucose-dependent insulinotropic polypeptide receptor

GLP-1 glucagon-like peptide-1

GLP-1R glucagon-like peptide-1 receptor

HbA1c hemoglobin A1c

HDL high-density lipoprotein

HDV hepatitis D virus

HR heart rate

HRT hormonal replacement therapy

HRQoL health-related quality of life

ΙB Investigator's Brochure

ICF informed consent form

ICH The International Council for Harmonisation of Technical Requirements for

Pharmaceuticals for Human Use

Informed consent A process by which a patient voluntarily confirms his or her willingness to participate

> in a particular study, after having been informed of all aspects of the study that are relevant to the patient's decision to participate. Informed consent is documented by

means of a written, signed and dated informed consent form.

interim analysis An interim analysis is an analysis of clinical study data, separated into treatment groups,

that is conducted before the final reporting database is created/locked.

INR international normalized ratio

investigational

product

A pharmaceutical form of an active ingredient or placebo being tested or used as a reference in a clinical trial, including products already on the market when used or assembled (formulated or packaged) in a way different from the authorized form, or marketed products used for an unauthorized indication, or marketed products used to gain further information about the authorized form.

IRB/IEC Institutional Review Boards /Independent Ethics Committees

ITT intent to treat: The principle that asserts that the effect of a treatment policy can be best

> assessed by evaluating on the basis of the intention to treat a patient (that is, the planned treatment regimen) rather than the actual treatment given. It has the consequence that patients allocated to a treatment group should be followed up, assessed, and analyzed as members of that group irrespective of their compliance to the planned course of

treatment.

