# 6. A Priori Statistical Methods

## 6.1. Populations for Analyses

For purposes of analyses, Table GPIA.6.1 defines the analysis sets.

 Table GPIA.6.1.
 Description of Analysis Datasets

Analysis Set	Description
Entered Participants	All participants who sign informed consent
Randomized Participants	All participants who are randomly assigned a study treatment
Modified Intent-to-Treat (mITT) Set	All randomly assigned participants who are exposed to at least 1 dose of study drug. Participants will be included in the treatment group they were randomized to.
Efficacy Analysis Set (EAS)	Data obtained during treatment period from mITT, excluding data after discontinuation of study drug (last dose date + 7 days).
Full Analysis Set (FAS)	Data obtained during treatment period from mITT, regardless of adherence to study drug.
Safety Analysis Set (SS)	Data obtained during the treatment period plus safety follow-up period from mITT, regardless of adherence to study drug.
Per Protocol Set (PPS)	Participants included in the randomized population who have completed Week 52 of study treatment without permanent discontinuation of IP and without significant protocol deviations through Week 52 that would significantly impact the primary objective.
	Treatment group will be defined on the basis of the treatment the participants actually receive.

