## 6.2. General Considerations

Statistical analysis of this study will be the responsibility of Eli Lilly and Company (Lilly) or its designee. Some analyses and summaries described in this analysis plan may not be conducted if not warranted by data (e.g., few events to justify conducting an analysis). Additional analyses of the data may be conducted as deemed appropriate.

Unless otherwise noted, tests of treatment effects will be conducted at a 2-sided alpha level of 0.05, and the confidence interval (CI) will be calculated at 95% 2-sided.

Unless specified otherwise, efficacy and safety will be assessed using the modified intention-totreat (mITT) population, and data will be analyzed based on the randomized treatment (that is, not the actual treatment received by the participant). For primary efficacy analysis, the efficacy analysis will be conducted using Efficacy Analysis Set (EAS). Safety analysis will be conducted using Safety Analysis Set (SS).

Summary descriptive statistics for continuous measures will include sample size, mean, standard deviation (SD), median, minimum, and maximum. The analysis model to make comparisons among treatment groups relative to continuous measurements assessed over time will be either analysis of covariance (ANCOVA) or a mixed model for repeated measures (MMRM).

Kaplan-Meier method will be used for estimation of cumulative event-free survival rates over time, and Cox proportional hazards regression analysis will be used to compare hazards rates among treatments.

Summary statistics for categorical measures (including categorized continuous measures) will include sample size, frequency, and percentages. Logistic regression will be used to examine the treatment difference in binary efficacy outcomes if there is a need to adjust for covariate. Otherwise, Fisher's exact test will be used to examine the treatment difference.

Summary statistics for discrete count measures will include sample size, mean, SD, median, minimum, and maximum.

Unless specified otherwise, baseline will be defined as the last available non-missing measurement during Visit 1 to Visit 2. For the safety related parameters, the definition of baseline and postbaseline are specified in Table GPIA.6.2.

Analysis Set	Analysis Type	Baseline	Postbaseline
SS	1.1) Treatment-	The baseline period is defined	Starts after the first dose of study
	Emergent Adverse	as the start of screening and	treatment and ends at the end of the

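### The Efficacy Analysis Set keeps weights taken after a permitted blinded switch from tirzepatide to placebo, which does not match the week-52 efficacy estimand

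*SAP*

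**What the plan says.** **EAS.** SAP 6.1 (Table GPIA.6.1) defines it as "Data obtained during treatment period from mITT, excluding data after discontinuation of study drug (last dose date + 7 days"). Protocol 10.2 (Table GPIA.4) has the same cut, at "discontinuation of study drug (last dose date + 7 days"). SAP 6.2 bases the primary efficacy analysis on the EAS and groups participants by randomised arm, "not the actual treatment received by the participant".

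**Estimand.** SAP 6.2 defines the efficacy estimand, for the type I error controlled objectives at 52 weeks, as the effect if randomised participants had stayed on their assigned treatment for all 52 weeks. SAP 6.5 places the type I error control on this estimand.

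**Dose reduction.** Protocol 7.4.2 permits one blinded reduction for intolerable gastrointestinal symptoms that persist despite counselling, symptomatic medication and a short interruption, after contact with the sponsor. It gives the case "10 mg or lower reduced to placebo, the lower dose will be maintained for the rest of the study". Discontinuation comes afterwards. If symptoms continue despite the other measures and "resumption at a lower dose of study drug, the participant should be discontinued from the study drug".

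**Meaning of study drug.** Protocol 5.1.1.2.2 has participants "inject the first dose of tirzepatide or placebo. The date and time of the first dose of study drug will be recorded". Protocol Appendix 1 defines investigational product as "A pharmaceutical form of an active ingredient or placebo being tested or used as a reference in a clinical trial".

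**Other handling.** SAP 6.12.1.3 deals with intercurrent events for the treatment regimen estimand only. SAP 6.12.1.1 fills in week-52 weights for the responder endpoint only when they are missing. SAP 6.10.2 makes counts of dose de-escalation optional.

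**The concern.** A tirzepatide participant moved to placebo is still taking study drug as the protocol uses the term. The EAS cut is not triggered, and the later weights are analysed as observed tirzepatide data. Yet that participant has left the randomised treatment, which the efficacy estimand supposes does not happen.

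Two people with the same intolerance are then handled in opposite ways. One who stops injecting has later data removed and treated as missing at random. One who is switched to placebo keeps those data in the analysis. At stake is what the primary estimate means; the likely direction of the discrepancy is attenuation. Because the count is optional, readers might also never learn how many people were affected.

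**Working it through.** **1. The plan's own power figure.** Inputs from SAP 5.1 (sample size) and protocol 10.1: 70 per arm, 25% dropout, difference 11 points, SD 11, two-sided alpha 0.025, and ≥5% responder rates of 25% and 90%. Evaluable per arm: 70 × 0.75 = 52.5, taken as 52. A two-sample t-test gives 99.7% power and the comparison of proportions gives over 99.9%. The stated figure of more than 90% is reproduced.

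**2. Time on substituted placebo.** Protocol 5.4 gives a "40-week treatment period at the dose achieved 10 mg and 32-week treatment period at the dose achieved 15 mg". So 15 mg is reached at week 52 − 32 = 20, and 12.5 mg starts one 4-week step earlier, at week 16. In the 15 mg arm, a switch to placebo during initial escalation therefore comes by about week 16 and leaves about 52 − 16 = 36 weeks or more on placebo. In the 10 mg arm the switch can come at any time, so the placebo period may be short.

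**3. Assumptions.** The documents give no switch rate. Let f be the share of an arm's week-52 participants who were switched. Values of 2%, 5% and 10% of 52 are 1.0, 2.6 and 5.2 people. Let c be the share of the 11-point effect that switchers would have had on continued drug. Assume full drift to the placebo mean after the switch. Under a revised cut at the last active dose, assume switchers are predicted at the arm mean, or as responders.

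**4. Error in the mean difference (points), f = 2 / 5 / 10%.** Current cut: −f × c × 11. Revised cut: +f × (1 − c) × 11.

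| c | Current cut | Revised cut |
|---|---|---|
| 1 | −0.22 / −0.55 / −1.10 | 0 / 0 / 0 |
| 0.5 | −0.11 / −0.28 / −0.55 | +0.11 / +0.28 / +0.55 |
| 0.25 | −0.06 / −0.14 / −0.28 | +0.17 / +0.41 / +0.83 |

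The errors are equal in size at c = 0.5.

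**5. Error in the ≥5% responder difference (points), f = 2 / 5 / 10%.** Current cut: −f × (true rate − 25). Revised cut: +f × (100 − true rate). The true rate is the switchers' rate on continued drug.

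| True rate | Current cut | Revised cut |
|---|---|---|
| 90% | −1.3 / −3.25 / −6.5 | +0.2 / +0.5 / +1.0 |
| 70% | −0.9 / −2.25 / −4.5 | +0.6 / +1.5 / +3.0 |
| 50% | −0.5 / −1.25 / −2.5 | +1.0 / +2.5 / +5.0 |
| 30% | −0.1 / −0.25 / −0.5 | +1.4 / +3.5 / +7.0 |

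They are equal in size where rate − 25 = 100 − rate, that is, at 62.5%. The documents give no ≥10% or ≥15% rates, so the same sum cannot be done for those endpoints.

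**6. Retained effect.** If some effect persists after the switch, the current-cut error is smaller. With c = 1 and half the effect retained, the loss is 0.11, 0.28 or 0.55 points.

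**7. Power under the current cut.** With f = 10%, c = 1 and full drift, the difference is 9.9. Adding the mixing variance gives a tirzepatide SD of √(121 + 0.10 × 0.90 × 121) = 11.48. Power is 98.6%, or 98.9% with the SD held at 11.

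**The case against.** **The revised cut may be no better.** On the assumptions above, the current cut is closer for the mean when c is below 0.5, and for ≥5% response when switchers' true rate is below 62.5%. People selected for intolerance may well lie there. This stands: a reader might infer that the revised cut reduces bias, and the documents do not support that. The prediction at the arm mean is itself an assumption, since the MMRM also uses switchers' earlier weights.

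**The illustration is extreme and the route narrow.** Full drift is the least favourable case, and the switch requires several failed measures and sponsor contact. Both stand.

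**The consequence is limited.** A reader might infer that the trial's conclusion or error control is at risk. The likely shift is towards no difference, power stays far above 90% across the range shown, and the SAP already plans a treatment regimen analysis in the Full Analysis Set (FAS) irrespective of adherence.

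**Week 20.** The same cut feeds the week-20 key secondary endpoint. A reader might call that a contradiction too, but SAP 6.2 defines the efficacy estimand only for week-52 objectives, so there is no week-20 definition to contradict.

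**Study drug might mean tirzepatide only.** That reading would close the gap, but it conflicts with protocol 5.1.1.2.2 and 7.4.2 and would leave the placebo arm without an EAS cut-off. It does not stand.

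**Unread material.** Protocol Appendix 9 and the disposition figure in 8.2.1 could not be read and might settle the matter.

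**Conclusion.** The mismatch is real in the readable text: a stated data rule produces data that the stated week-52 efficacy estimand excludes. It reaches both co-primary endpoints and the week-52 key secondary endpoints (≥10%, ≥15%, waist circumference). Its size is unknown because no switch rate is given, and it is probably small. The figures above are illustrations that rest on assumed switch rates and full drift.

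The gain from correcting it is agreement between analysis and estimand, equal handling of switchers and discontinuers, and transparency; a smaller error is not proven. Severity is minor to moderate. Confidence is medium, given the unread figures.

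**What to change.** Change the analysis definition only, before unblinding:

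1. For participants randomised to tirzepatide, end EAS data at the earlier of last study-drug dose + 7 days and last active tirzepatide dose + 7 days. This matches how discontinuers are already handled. Keep placebo-arm data after a sham reduction.
2. Run the current cut as a prespecified sensitivity analysis and report both.
3. Make the count of participants switched to placebo, by arm, mandatory.
4. Leave the FAS analysis and the clinical rule unchanged.

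If Appendix 9 or the disposition figure already covers the point, a cross-reference in the EAS definition is enough.

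**Cost.** One definition changes in two tables, with one extra run. It carries into every EAS analysis, including the other secondary, exploratory and subgroup analyses. Protocol 10.3.1 would require an amendment if the primary data cut counts as a principal feature. The last active dose date must be linked from the IWRS dose adjustments (7.4.2) and participant-recorded dosing (7.2.1). The main statistical downside is that more data rest on missing-at-random predictions, and in the tirzepatide arms only.

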## 6.2. General Considerations

Statistical analysis of this study will be the responsibility of Eli Lilly and Company (Lilly) or its designee. Some analyses and summaries described in this analysis plan may not be conducted if not warranted by data (e.g., few events to justify conducting an analysis). Additional analyses of the data may be conducted as deemed appropriate.

Unless otherwise noted, tests of treatment effects will be conducted at a 2-sided alpha level of 0.05, and the confidence interval (CI) will be calculated at 95% 2-sided.

Unless specified otherwise, efficacy and safety will be assessed using the modified intention-totreat (mITT) population, and data will be analyzed based on the randomized treatment (that is, not the actual treatment received by the participant). For primary efficacy analysis, the efficacy analysis will be conducted using Efficacy Analysis Set (EAS). Safety analysis will be conducted using Safety Analysis Set (SS).

Summary descriptive statistics for continuous measures will include sample size, mean, standard deviation (SD), median, minimum, and maximum. The analysis model to make comparisons among treatment groups relative to continuous measurements assessed over time will be either analysis of covariance (ANCOVA) or a mixed model for repeated measures (MMRM).

Kaplan-Meier method will be used for estimation of cumulative event-free survival rates over time, and Cox proportional hazards regression analysis will be used to compare hazards rates among treatments.

Summary statistics for categorical measures (including categorized continuous measures) will include sample size, frequency, and percentages. Logistic regression will be used to examine the treatment difference in binary efficacy outcomes if there is a need to adjust for covariate. Otherwise, Fisher's exact test will be used to examine the treatment difference.

Summary statistics for discrete count measures will include sample size, mean, SD, median, minimum, and maximum.

Unless specified otherwise, baseline will be defined as the last available non-missing measurement during Visit 1 to Visit 2. For the safety related parameters, the definition of baseline and postbaseline are specified in Table GPIA.6.2.

Analysis Set	Analysis Type	Baseline	Postbaseline
SS	1.1) Treatment-	The baseline period is defined	Starts after the first dose of study
	Emergent Adverse	as the start of screening and	treatment and ends at the end of the
	Events	ends prior to the first dose of	study period (including off-drug follow
		study treatment (typically at	up visit).
		Week 0).	
SS	1.2) Treatment-	Baseline will include all	Postbaseline will be defined as
	Emergent	scheduled and unscheduled	measurements after Visit 2. All
	Abnormal Labsa,	measurements during the	scheduled and unscheduled
	Vital Signs, and	baseline period (Visit 1 to	measurements will be included.
	ECGs.	Visit 2)	
SS	1.3) Change from	The last scheduled and	Postbaseline will be defined as above
	Baseline to Week	unscheduled non-missing	(1.2). Only scheduled visits will be
	xx and to Last	assessment recorded during the	included. The early discontinuation
	Postbaseline for	baseline period defined above	(ED) visits are considered scheduled
	Labs a , Vital Signs,	(1.2).	visits.
	and ECGs.		

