5.1.1.2.3. Safety Follow-up Period

Visit 801

All participants are required to complete Visit 801, a safety follow-up visit. Participants discontinuing the study early and performing an early discontinuation (ED) visit will also be asked to perform the safety follow-up visit. During the safety follow-up period, participants will not receive study drug. Participants are also required to return any remaining study diaries to the study site at the end of this period.

For participants who discontinue or complete the study within the first 52 weeks, Visit 801 (safety follow-up visit) should be performed 4 weeks after the last treatment visit (Visit 99 or 15, respectively) or 4 weeks after the ED visit for those who decline to return for Visit 99.

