9.4.4. Immunogenicity Assessments

Where local regulations and ERBs allow, blood samples for immunogenicity testing will be collected to determine antibody production against tirzepatide as specified in the Schedule of Activities (Section 2).

At the visits and times specified in the Schedule of Activities (Section 2), blood samples will be collected to determine antibody production against tirzepatide. To interpret the results of immunogenicity, a PK sample will be collected at the same time points as the immunogenicity sample. All samples for immunogenicity should be taken predose when applicable and possible. In the event of systemic drug hypersensitivity reactions (immediate or nonimmediate), additional unscheduled samples should be collected as detailed in Appendix 6 (Hypersensitivity Events). Instructions for the collection and handling of blood samples will be provided by the sponsor. Sample collected at Visit 801 will assess immunogenicity at washout of tirzepatide (5 half-lives post end of treatment).

Immunogenicity will be assessed by a validated assay designed to detect and titer antidrug antibody (ADA) in the presence of tirzepatide at a laboratory approved by the Sponsor. Samples with detected ADA will be tested for cross-reactive binding to native GIP and GLP-1. Antibodies may be further evaluated for their ability to neutralize the activity of tirzepatide. In vivo laboratory indicators for glycemic control (fasting blood glucose and HbA1c), effect on weight loss and PK will be utilized to detect potential neutralizing effect of ADA against tirzepatide.

Treatment-emergent antidrug antibodies are defined in Section 10.3.6.

ADA and hypersensitivity samples will be stored as per local regulation/EC requirement. Samples will be immediately destroyed once tirzepatide is launched for weight management indication or there is no further request on testing the samples from China authority.

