## 6.13. Safety Analyses

Unless specified otherwise, safety assessments will be based on the SS (Table GPIA.6.1). All events that occur between the first dose date of study drug and the end date of study participation will be included, regardless of the adherence to study drug.

The statistical assessment of homogeneity of the distribution of categorical safety responses between tirzepatide doses and placebo will be conducted using Fisher's exact test, unless specified otherwise.

For the selected continuous safety parameters, the mean change from baseline differences vs. placebo will be assessed via an MMRM using REML. Data from scheduled visits will be utilized for this analysis unless specified otherwise, the model for the analysis during 52 weeks treatment period will include sex, presence of comorbidities at randomization, treatment group, visit and treatment-by-visit interaction as fixed effects, and baseline value of the safety parameter as a covariate. To model the covariance structure within participants, the unstructured covariance matrix will be used. If this model fails to converge, the covariance structures specified in Section 6.12.1.1 will be tested in order until met convergence. If the data does not warrant the MMRM model, then ANCOVA model will be conducted.

For selected safety parameters, time-to-first-event analysis via the Cox-proportional hazards model may be conducted. Participants without the event will be censored at the end of study participation. For participants experiencing the event, the "time-to-first-event" will be the time (in days) from first dose to first occurrence of the event.

Where necessary, the rate of events will be analyzed using a generalized linear mixed-effects model assuming the number of events follow a negative binomial distribution and with treatment as a fixed effect. The logarithm of days during the active treatment period will be adjusted as an offset to account for possible unequal treatment duration of follow-up between participants.

Unless otherwise specified, all the analyses listed in this section will be conducted using SS in the postbaseline period: up to 52 weeks treatment period plus the safety follow-up (Visit 801, if applicable) for all randomized participants.

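### SAP Table GPIA.6.2, row 1.3: Last Postbaseline for labs, vital signs and ECGs has no end point, so it takes in the off-drug Visit 801 and understates drug effects that reverse

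*SAP*

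**What the plan says.** **The row.** SAP Table GPIA.6.2 (Section 6.2) gives baseline and postbaseline windows for three types of safety analysis, all on the SS. Row 1.3 is change from baseline to Week xx and to Last Postbaseline for labs, vital signs and ECGs. Its window is set by back-reference: "Postbaseline will be defined as above". Row 1.2, to which it points, gives only a starting point, "measurements after Visit 2. All", and no end. Row 1.3 then keeps scheduled visits only and counts ED visits as scheduled.

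**The analysis set and default window.** SAP Section 6.1 defines the SS as "Data obtained during the treatment period plus safety follow-up period from mITT, regardless of adherence to study drug". SAP Section 6.13 sets the default period for its safety analyses as "up to 52 weeks treatment period plus the safety follow-up (Visit 801, if" applicable).

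**Visit 801.** Protocol Section 5.1.1.2.3 states "All participants are required to complete Visit 801, a safety follow-up visit", and adds that no study drug is given in that period. The Schedule of Activities gives Visit 801 its own column, with vital signs, ECG, chemistry, lipids, HbA1c, pancreatic enzymes, calcitonin and hematology marked. Protocol Section 9.4.4 describes the drug's status then: "Sample collected at Visit 801 will assess immunogenicity at washout of tirzepatide (5 half-lives post end of treatment"). Protocol Section 5.4 says the follow-up period serves to assess what happens when drug is stopped.

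**The concern.** A reader of a safety report will usually take a last-postbaseline change as an end-of-treatment value. Under row 1.3 it is not one. For anyone who attends Visit 801, it is a value taken after weeks without drug. If a change in heart rate, blood pressure, an ECG interval, a pancreatic enzyme or a liver test fades after stopping, this summary shows less of it than was present on treatment. The error runs toward no difference from placebo, which is the unfavourable direction for a safety summary.

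The summary also mixes unequal off-drug intervals. Completers are about 4 weeks past their last treatment-period visit. Under Protocol Section 5.1.1.2.3, an early discontinuer who returns for Visit 99 has Visit 801 four weeks after that, which can be many months after the last dose.

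**Working it through.** The plan states no figure for this summary, so there is none to reproduce. The check is a reading of the text, followed by an illustration of size.

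**1. Is Visit 801 inside the window?**
- Start: after Visit 2 (row 1.2, carried into row 1.3).
- End: none in row 1.2 or 1.3. The SS and the Section 6.13 default both run through safety follow-up.
- Restriction: scheduled visits only. Visit 801 is in the Schedule of Activities and collects these measurements.
- Exclusion of Visit 801: none found.

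As written, Visit 801 is inside the window and is the last value for every attendee.

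**2. How far off drug is it?** Drug remaining is 0.5^(days ÷ half-life).
- At the 5 half-lives stated in Protocol Section 9.4.4: 0.5^5 = 3.1%.
- Cross-check: Protocol Appendix 7 equates 5 half-lives plus 90 days with about 4 months. Taking 4 months as 120 days, (120 − 90) ÷ 5 = 6 days per half-life.
- At 28 days: 0.5^(28/6) = 3.9%. At 35 days: 0.5^(35/6) = 1.8%. At 21 days, the early edge of the ±7-day visit window counted from a last dose at the final visit: 0.5^(21/6) = 8.8%.

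The protocol's washout wording agrees with its other figures.

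**3. Early discontinuers.** Suppose the ED visit is at Week 12 and the participant returns for Visit 99 at Week 52. Visit 801 is then at about Week 56, and 56 − 12 = 44 weeks after the ED visit. The Schedule marks no vital signs, ECG or chemistry at Visit 99. If no other visits are attended in between, row 1.3 passes over the ED value in favour of the one 44 weeks later.

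**4. How much of an on-drug mean change would the summary keep?** Let p be the share of last values that come from Visit 801, and r the share of the on-drug effect still present then.

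Share kept = 1 − p(1 − r)

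Both inputs are assumptions. For p, the range runs from 0.75 (the 25% dropout used in the sample size section, 70 × 0.75 = 52.5 per arm, as a stand-in for attendance) to 1 (everyone attends, as required). The documents give no value of r for any parameter.

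| | r = 0 (full reversal) | r = 0.5 | r = 1 (no reversal) |
|---|---|---|---|
| p = 0.75 | 25% | 62.5% | 100% |
| p = 0.90 | 10% | 55% | 100% |
| p = 1.00 | 0% | 50% | 100% |

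The formula treats participants without a Visit 801 value as on drug at their last value and as having the same effect as attendees. Some will have stopped drug but kept attending, as Protocol Section 8.1.1 asks. For effects that reverse, that lowers the share kept further.

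**5. What the rest of the plan does.** Change to Week 52 and to other named visits is unaffected. The SAP already limits several analyses to the treatment period or separates the periods: liver test elevations (6.13.3.4.2), immunogenicity (6.13.3.6.2), the QTcF increase (6.13.5), and the laboratory MMRM or ANCOVA (6.13.6).

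**The case against.** **The window is inferred.** Row 1.1 names the off-drug visit ("study period (including off-drug follow" up visit); rows 1.2 and 1.3 do not. Row 1.3 takes care to count ED visits, which would seldom supply the last value if Visit 801 always superseded them. The authors may have meant the treatment period. This stands as evidence of ambiguity. But the SS definition and the Section 6.13 default both point to inclusion, and a programmer following the text would include Visit 801.

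**No endpoint is at stake.** A reader might infer that a safety endpoint has been set at washout and that on-drug changes are hidden. The documents do not support that. Last Postbaseline is named only in this definitions table; Sections 6.13.4 to 6.13.6 call for no test or model of it. On-drug changes remain visible elsewhere:
- by-visit change for labs, vital signs and ECGs;
- the 52-week MMRM for selected safety parameters;
- maximum and minimum analyses of vital signs;
- maximum postbaseline categories for pancreatic enzymes and calcitonin;
- liver elevations during the treatment period.

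This stands, and it limits the consequence. It does not change what the row 1.3 summary measures. The vital-sign model is optional, the laboratory model covers selected tests, and Section 6.2 says not every analysis will appear in the CSR.

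**Low drug level is not low effect.** A reader might also infer that only about 3% of any effect survives because about 3% of the drug does. The documents do not link concentration to reversal of any lab, vital sign or ECG effect, so no single figure for the loss can be defended. This stands.

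**Conclusion.** The point holds as a minor specification gap. As written, Last Postbaseline in row 1.3 is an off-drug value for most participants, and it understates on-drug changes that reverse after stopping. The reading of the window rests on the text alone. The size does not: it runs from total loss of the effect in this one summary to none, depending on Visit 801 attendance and on reversal, neither of which the documents give. Slowly reversing parameters will be little affected. Sample size, power and type 1 error are not involved.

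**What to change.** In SAP Table GPIA.6.2, row 1.3:
1. End Last Postbaseline at the last scheduled measurement, ED included, of the 52-week treatment period.
2. State whether values after study drug discontinuation count. Discontinuers are asked to keep attending visits, so ending the window at Week 52 does not by itself give an on-drug value. Either choice can be defended, but it should be written down.
3. Show change from baseline to Visit 801 separately, labelled as an off-drug summary.

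Leave rows 1.1 and 1.2 on the full window, where any-time events and abnormalities belong. The cost is one row of SAP wording and one extra summary column, with no new data. Made before unblinding, the change also avoids a later choice of safety window with results in view.
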